8.3. Subject Withdrawal Criteria

Subjects will be informed that they have the right to withdraw from the study at any time for any reason, without prejudice to their medical care. Study drug must be permanently discontinued and the subject withdrawn from the study for any of the following TEAEs, with the subject managed as indicated:

- **Palmar-plantar Erythrodysesthesia (PPE):** For mild to moderate symptoms of PPE (e.g., redness, pain, or scaling of hands or feet), study drug should be interrupted and symptomatic measures, including hand cream such as “Udder Cream,” instituted immediately. Study drug may be resumed after resolution of symptoms; study drug should be discontinued permanently if PPE Grade ≥ 2 recurs after study drug is resumed. Study drug should also be permanently discontinued at the first sign of significant/severe, redness, pain, or scaling of hands or feet, and symptomatic measures instituted immediately.
- **Dyspnea or suspected pneumonitis:** Study drug should be permanently discontinued for subjects with shortness of breath or other respiratory symptoms that are otherwise unexplained. An unscheduled SARS-CoV-2 test should be done if a subject develops dyspnea or pneumonitis. The subject is to be carefully monitored for improvement. In the event that symptoms worsen or present as more than mild intensity, immediate referral to a qualified pulmonologist for definitive diagnosis and treatment should be undertaken.
- **Visual symptoms (including keratitis):** Study drug should be permanently discontinued at the first sign of significant redness (erythema), pain, or dryness affecting one or both eyes. Symptomatic measures, including moisturizing eye drops, should be instituted. In the event that symptoms worsen or present as more than mild, immediate referral to a qualified ophthalmologist or optometrist should be undertaken.

- **Suspected drug-induced liver injury (DILI):** Study drug intake should be managed according to the different laboratory and clinical circumstances itemized in [Appendix A](#) for subjects with suspected DILI.

Refer to the Study Manual for additional details regarding the assessment and management of these events.

Furthermore, the Investigator also has the right to withdraw subjects from the study for any of the following reasons:

- Progression of underlying disease that, in the opinion of the Investigator, precludes further study treatment.
- Occurrence of any other unacceptable AE.

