- Study drug interruption for any reason for >15 days.
- Subject requires use of a prohibited concomitant medication or therapy.
- General or specific changes in the subject's condition unacceptable for further treatment within the study parameters, in the judgment of the Investigator.
- Noncompliance.
- Lost to follow-up.
- Subject withdrawal of consent.
- Sponsor request.

At the time of study withdrawal, all study procedures outlined for the Early Termination visit should be completed ([Figure 1: Study Design](#)

Abbreviations: CAP = controlled attenuation parameter; MRI = magnetic resonance imaging; NAS = nonalcoholic fatty liver disease activity score; NASH = nonalcoholic steatohepatitis; PDFF = protein density fat fraction; [REDACTED] PO = orally; QD = once daily.

Table 2). The primary reason for a subject's withdrawal from the study is to be recorded in the electronic case report form (eCRF) together with explanatory comment where required. If the subject is not on site when the decision to withdraw the subject from the study is confirmed, the subject should return to the clinic to undergo the Early Termination visit as soon as possible thereafter.

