APPENDIX A. ALGORITHM FOR EVALUATING SUBJECTS FOR POTENTIAL DRUG-INDUCED LIVER INJURY

During the study, aminotransferase elevations are to be managed as follows:

1. Isolated aminotransferase elevation (i.e., total bilirubin - normal):

ALT or AST	Event during the study	Action
Baseline ALT and AST within normal range	Increase $\geq 5 \times$ ULN	Repeat liver profile (AST, ALT, bilirubin) and PT/INR within 2 to 3 business days from the date results are received for review. Monitor the subject as per “close observation” definition* in the DILI guidance.
ALT or AST above normal range at Baseline	Increase $\geq 3 \times$ Baseline result, but no liver related symptoms (e.g., anorexia, nausea, vomiting, right upper quadrant pain, pruritus, cholestasis)	Interrupt study drug for at least 15 days. Initiate potential DILI evaluation for alternative etiologies, and repeat liver profile and PT/INR within 2 to 3 business days from the date results are received for review, and place subject under “close observation” as defined in the DILI guidance.
ALT or AST above normal range at Baseline	Increase $\geq 3 \times$ Baseline result, and subject experiences liver- related symptoms (e.g., anorexia, nausea, vomiting, right upper quadrant pain, pruritus, cholestasis)	Interrupt study drug for at least 15 days. Initiate potential DILI evaluation for alternative etiologies, and repeat liver profile and PT/INR within 2 to 3 business days from the date results are received for review, and place subject under “close observation” as defined in the DILI guidance.

Abbreviations: ALP = alkaline phosphatase; ALT = alanine aminotransferase; AST = aspartate aminotransferase; DILI = drug-induced liver injury; GGT = gamma-glutamyltransferase; INR = international normalized ratio; PT = prothrombin time; ULN = upper limit of normal.

*Close observation as defined in the FDA DILI guidance (i.e., laboratory testing and physical examination 2 to 3 times per week. Study drug is to be restarted only if a firm alternative etiology is “identified” and the liver tests return to ‘baseline’ levels).

Note the following:

The ‘baseline’ result for any laboratory parameter is the average of the Screening visit result, the Day 1 visit result and any unscheduled visit that occurred during the Screening period.’

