Study drug interruption refers to cessation of study drug intake, but with the possibility that intake may re-start at a later date if certain requirements described in this appendix are confirmed.

Conversely, study drug discontinuation refers to cessation of study drug intake and without the possibility that intake may restart at a later date. However, such a subject should remain in the study, continue to undergo ‘close observation’ where required, and other scheduled study assessments.

If a subject sustains a liver test elevation but remains eligible to continue study drug intake in parallel with ‘close observation’, and ‘close observation’ is not possible then study drug intake should be interrupted until it is possible for the subject to undergo further assessment.

Close observation as defined in the FDA DILI guidance i.e., laboratory testing and physical examination 2 to 3 times per week. Study drug is to be restarted only if a firm alternative etiology is “identified” and the liver tests return to ‘baseline’ levels.

2. Elevation of aminotransferase and total bilirubin or cholestatic liver test markers:

Analyte	Event during the study	Action
TB + AST or ALT	↑ TB >2 mg/dL and ↑ ALT or ALT \geq 3 × Baseline or 5 × ULN (whichever comes first)	Interrupt study drug for at least 15 days. Initiate potential DILI evaluation for alternative etiologies. Repeat liver profile and PT/INR within 2 to 3 business days from the date results are received for review, and place subject under “close observation” as defined in the DILI guidance.
TB, ALP, or GGT	↑ TB >2 mg/dL and ALP or GGT ↑ >2 × ULN	Study drug can be re-started only if a firm competing etiology is identified and the liver tests return to Baseline levels.
TB OR INR + symptoms (regardless of any magnitude AST/ALT elevation)	Elevation ↑ TB >2 mg/dL OR INR \geq 1.5 and Indicators of immunological reaction (i.e., rash or >5% eosinophilia), or appearance of liver-related symptoms, e.g., anorexia, nausea, vomiting, right upper quadrant pain, pruritus, cholestasis.	Permanently discontinue study drug. Initiate potential DILI evaluation for alternative etiologies. Repeat liver profile and PT/INR within 2 to 3 business days from the date results were received for review, and place subject under “close observation” as defined in the DILI guidance.

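### The lead-in of Protocol Section 8.3 orders a permanent stop and study withdrawal for four adverse events, but Appendix A keeps subjects stopped for liver injury in the study, and Appendix A and the PPE bullet allow restart

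*Protocol*

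**What the plan says.** **Lead-in of Protocol 8.3.** For PPE, dyspnea or suspected pneumonitis, visual symptoms and suspected DILI, the rule is "Study drug must be permanently discontinued and the subject withdrawn from the study for any of the following TEAEs". The sentence then adds "with the subject managed as indicated" and leads into four event-specific bullets.

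**PPE bullet of 8.3.** For mild to moderate symptoms, "study drug should be interrupted and symptomatic measures" are to be started, and "Study drug may be resumed after resolution of symptoms". A permanent stop is reserved for recurrence at Grade 2 or above after restart, or for significant or severe signs.

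**DILI bullet of 8.3.** "Study drug intake should be managed according to the different laboratory and clinical circumstances itemized in" Appendix A. The bullet covers study drug intake and says nothing about study participation.

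**Appendix A.** Depending on the liver findings, the action is monitoring, interruption ("Interrupt study drug for at least 15 days") with restart on conditions, or permanent discontinuation. On a subject whose drug is permanently stopped, it says: "However, such a subject should remain in the study, continue to undergo" close observation where required, together with the other scheduled assessments.

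**Second list in 8.3.** The Investigator has the right to withdraw a subject for several reasons, one of which is "Study drug interruption for any reason for >15 days".

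**Protocol 7.3.** Dose modification is barred for those Section 8.3 events that require permanent discontinuation. Interruptions may be allowed, with a cross-reference to both Appendix A and 8.3.

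**The concern.** Study drug and study participation are separate decisions, and the lead-in of 8.3 settles both with one mandatory sentence. Read literally, it takes a subject with suspected DILI out of the study. Appendix A wants the same subject kept in, with scheduled assessments continuing. Read literally, it also stops drug for good in a subject with mild PPE, whom the bullet below allows to resume. With about 100 centers planned, different readings are likely.

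What is at stake statistically depends on which decision is affected. The primary analysis counts a subject who stops treatment before Week 42 as a non-responder, and the mITT population requires at least 42 weeks of treatment. The drug decision can therefore move a subject between outcome categories and between analysis sets. The participation decision determines how much off-treatment safety and secondary-endpoint follow-up exists for subjects who stopped because of an adverse event.

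**Working it through.** This is a comparison of texts. No figure in the plan is in dispute, so there is none to reproduce.

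**Step 1. Compare the lead-in with the text for each event.** In every row the lead-in says permanent stop and withdrawal from the study.

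| Event | Event-specific text on drug | Event-specific text on participation | Conflict with lead-in |
|---|---|---|---|
| PPE | Interrupt and possibly resume; permanent stop only in stated cases | Not stated; resumption implies staying | Drug |
| Dyspnea or pneumonitis | Permanent stop | Not stated | None on drug |
| Visual symptoms | Permanent stop | Not stated | None on drug |
| Suspected DILI | Monitoring, interruption with conditional restart, or permanent stop (Appendix A) | Stays in the study after a permanent stop (Appendix A) | Drug and participation |

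The drug conflict is therefore confined to PPE and suspected DILI. The one explicit conflict on participation is for suspected DILI.

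**Step 2. Ask whether the qualifying clause resolves it.** The words "with the subject managed as indicated" let a reader treat the bullets as governing, which helps on study drug. They do not settle participation. The DILI bullet sends the reader to Appendix A only for drug intake, and no bullet in 8.3 says that a discontinued subject stays in the study.

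**Step 3. Check the 15-day rules.** Appendix A sets a minimum interruption of 15 days. The Section 8.3 reason applies above 15 days and is discretionary. An interruption of exactly 15 days meets the minimum and does not trigger the reason. From day 16 the Investigator may withdraw the subject but need not. Both texts can be followed, so this is a tension and not a strict contradiction. It still matters, because restart also requires a firm alternative cause and a return of liver tests to baseline, so a compliant interruption may run past 15 days.

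**Step 4. Trace each decision to the analyses.**

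- *Restart or permanent stop before Week 42.* Under Protocol 13.2.1 and SAP 7.11 and 9.1.1, a permanent stop before Week 42 means non-response. Under Protocol 13.4.2.2 and SAP 6, it also means exclusion from the mITT population. A subject who restarts, completes at least 42 weeks and has an evaluable biopsy can be a responder and an mITT member. This decision can change the primary result.
- *Stay or withdraw after a permanent stop before Week 42.* The subject is a non-responder and outside the mITT population either way. The histology-based secondary responder endpoints follow the same rule (SAP 7.11). The primary endpoint does not change. What changes is whether later scheduled assessments take place, such as liver tests, lipids, FibroScan and MRI-PDFF. SAP 7 includes data only up to study completion or withdrawal.

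**The case against.** The strongest defence is that the lead-in is only badly drafted. Its closing clause points to the bullets, the PPE bullet grades the response, and the DILI bullet defers to Appendix A. Section 7.3 speaks of those Section 8.3 events that require permanent discontinuation, which implies that not all of them do. Resuming drug after an adverse-event hold also needs consultation with the Investigator, the CRO's Medical Monitor and the Sponsor's Chief Medical Officer (Protocol 7.1, 7.3 and 9.5), so sites do not decide alone. Section 8.3 further refers to a Study Manual that is not among the documents.

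Much of this stands for study drug: a careful reader can recover a workable rule, although the mandatory sentence remains. It does not stand for participation, because nothing cited there says that a subject stopped for DILI stays in the study.

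It is also fair to say that withdrawal does not end all safety follow-up. An Early Termination visit is required (8.3), and adverse events are collected for 28 days after the last dose (12.2.1.1). Treatment-emergent serious events and possibly related events are followed until resolved or stable (12.2.5). Appendix A requires follow-up of subjects who meet its closing discontinuation criteria until the abnormalities stabilize or normalize. What withdrawal loses is the later scheduled visits.

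A reader might try to size the effect from the earlier study in Protocol 5.2, where 3 of 21 treated subjects in China had PPE. That gives 3/21 = 14.3%, or 0.143 × 108 = 15.4 active subjects here. If all were stopped, the 40% active response would become 40% × (1 − 0.143) = 34.3%. The documents do not support this figure:

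- It leaves out the 68 treated US subjects, for whom no PPE count is given. The US events listed as most common go down to 4 subjects each and do not include PPE. Assuming 0 to 3 US cases, the pooled rate is 3/89 to 6/89, or 3.4% to 6.7%. That is about 4 to 7 of 108, and a response of about 38.7% to 37.3%.
- It assumes that every case is stopped before Week 42 against the PPE bullet, that none would have been stopped permanently under that bullet anyway, and that these subjects respond at the average rate.
- All events in the China cohort resolved without dose adjustment.

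The pooled range shares the same assumptions, apart from the case count. It shows how far the answer depends on them and is not an estimate.

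**Conclusion.** The inconsistency is real and should be corrected. It has two parts. On participation, the Section 8.3 lead-in and Appendix A give opposite instructions for a subject permanently stopped for suspected DILI, and no other text resolves this. On study drug, the lead-in conflicts with the PPE bullet and with Appendix A; the qualifying clause and Section 7.3 soften this conflict without removing it.

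A reader might infer that all four events are affected, or that the two 15-day rules force a site to break one of them. Neither follows. The dyspnea and visual-symptom bullets agree with the lead-in on drug, and the 15-day withdrawal reason is a right and not a duty.

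No size of effect can be derived from the documents. The number of subjects affected, how sites would read the text, and when the events would occur are not given. What can be said is directional: the drug reading can change responder status and mITT membership, while the participation reading affects only later scheduled safety and secondary-endpoint data once drug has been stopped before Week 42.

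**What to change.** Reconcile five pieces of text: the lead-in of 8.3, its PPE bullet, its DILI bullet, the 15-day withdrawal reason and Appendix A. For each event, state one outcome for study drug (continue, interrupt with the conditions for restart, or stop permanently). State separately one outcome for study participation (remain with named assessments, or withdraw). Say how an Appendix A interruption that runs past 15 days relates to the Investigator's right to withdraw. Check that the reference in 7.3 to events requiring permanent discontinuation still points to an identifiable set. Which clinical rule applies is for the sponsor's clinical team to decide; the statistical need is only that it be stated once and consistently.

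The eCRF was not available for this review. If it does not already do so, it should record the end of treatment and the end of study participation as separate events, each with its own reason.

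The cost is a protocol clarification and a notice to sites. Sample size, endpoints and analysis methods do not change.

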9. TREATMENT OF SUBJECTS

9.1. Description of Study Drug

9.1.1. TVB-2640

TVB-2640 is a small-molecule, orally-bioavailable, reversible inhibitor of the human FASN enzyme. TVB-2640 has a molecular formula of C₂₇H₂₉N₅O and a molecular weight of 440.

TVB-2640 immediate-release formulation will be supplied for PO QD administration as 25- and 50-mg strength uncoated tablets.

9.1.2. Placebo

Placebo tablets that conform to the appearance, shape, and size of the TVB-2640 25-mg and 50-mg strength tablets will be used during this study.

9.2. Study Drug Packaging and Labeling

TVB-2640 will be packaged in bulk, screw-top plastic bottles containing 100 tablets.

TVB-2640 will be labeled in accordance with applicable regulatory requirements. Study drug labels will not bear any statement that is false or misleading in any manner or represents that the study drug is safe or effective for the purposes for which it is being investigated.

9.3. Study Drug Storage

TVB-2640 drug product and placebo should be stored in a secure, limited-access storage area at room temperature. Further study drug storage conditions and requirements will be provided in the study's Pharmacy Manual.

9.4. Study Drug Accountability

The US Food and Drug Administration (FDA) and other applicable regulatory authorities require accounting of all investigational drug received by each study center. Records of drug disposition required include the date received by the center, date administered, quantity administered, and the subject to whom study drug was administered. The Investigator is responsible for the accountability of all used and unused study drug containers and unused study drug.

Study drug (and placebo) will be provided to the investigational site. Site personnel will acknowledge receipt of the study drug using interactive response technology (IRT) to confirm the shipment condition and content. If a damaged shipment is received and/or a temperature excursion has been incurred, site personnel will notify the Sponsor/CRO and follow the guidelines according to the current version of the study's Pharmacy Manual.

The designated personnel will maintain accurate records of the study drug throughout the clinical study, including the inventory delivered to the study center, the use by each subject, the reconciliation of all delivered study drug, and the return of unused study drug as specified in the current version of the Pharmacy Manual.

The study monitor should check the study supplies at each study center at any time during the study. It is the responsibility of the study monitor to ensure that the Investigator (or designee) has correctly documented the amount of the study drug received, dispensed, and returned on the dispensing log that will be provided to site staff. Details will be provided in the Pharmacy Manual.

A full drug accountability log will be maintained at the study center at all times. The study monitor will arrange collection of any unused study drug. The study monitor will also perform an inventory of study drug at the close-out visit to the study center. All discrepancies must be accounted for and documented.

9.5. Study Drug Dose and Administration

All subjects will receive study drug PO QD for 52 weeks or until the final on-study investigation (MRI-PDFF and/or liver biopsy). The first dose of study drug should be taken at the study site under supervision of study staff.

In the event a subject is unable to complete the end of treatment MRI-PDFF and/or liver biopsy within the protocol-specified window (Week 52 +/- one week), extended dosing is permitted to maintain continuous dosing up to the time both assessments are completed, to a maximum total of 56 weeks of dosing. In this instance, the Follow-up visit at Week 56 for posttreatment safety and efficacy assessments is to be adjusted to occur four weeks after the last dose (+/- one week).

In the instance of a dose hold due to an AE or SAE, the decision to resume study drug will require consultation with the Investigator, the CRO's Medical Monitor, and the Sponsor's Chief Medical Officer.

Each QD dose of study drug is to be taken at the same time of day in the evening with or without food, with each dose separated by approximately 24 hours (± 4 hours).

Subjects will receive one of the following each day, based on their blinded treatment assignment:

- **Placebo:** one placebo tablet matching the 50-mg TVB-2640 tablet and one placebo tablet matching the 25-mg TVB-2640 tablet
- **TVB-2640 50 mg:** one 50-mg TVB-2640 tablet and one placebo tablet matching the 25-mg TVB-2640 tablet

If a dose adjustment for an individual subject is approved as described in Section 7.3, the subject will continue to receive 2 tablets QD as follows to preserve the study blind (see the Pharmacy Manual for additional details):

- **Dose adjustment from TVB-2640 50 mg to TVB-2640 25 mg:** one 25-mg TVB-2640 tablet and one placebo tablet matching the 50-mg TVB-2640 tablet
- **Dose adjustment for those randomized to placebo:** there will be no change in the size or number of placebo tablets. To maintain the blind, the subject will be provided with new study drug bottles

9.6. Treatment Assignment, Randomization, Blinding, and Unblinding

This will be a double-blind, randomized study. Subjects will be centrally assigned to randomized study treatment using an Interactive Web-based Response System (IWRS). Study medication will be dispensed at the study visits summarized in the Schedule of Assessments (Figure 1:

Study Design

Abbreviations: CAP = controlled attenuation parameter; MRI = magnetic resonance imaging; NAS = nonalcoholic fatty liver disease activity score; NASH = nonalcoholic steatohepatitis; PDFF = protein density fat fraction; [REDACTED] PO = orally; QD = once daily.

Table 2). Returned study drug should not be redispensed.

All subjects, Investigators, the Sponsor, and the CRO will be blinded to the treatment assignment of each individual subject. Members of the IDMC and the IDMC's independent statistician will be unblinded to treatment assignment as needed. In addition, specific vendors whose role in study conduct requires them to be unblinded (e.g., personnel operationally associated with the IWRS) may also be unblinded.

Subjects will be randomized to achieve a 2:1 ratio with approximately 108 subjects on TVB-2640 50 mg and approximately 54 subjects on placebo. Dynamic allocation will be used for the randomization, stratified by 3 factors: T2DM status (yes or no), region (North America or not North America), and amount of fibrosis (F2 or F3).

In the event that emergency unblinding is required for a given subject because of AEs or concerns for the subject's safety or well-being, the Investigator may request a code from the CRO in order to break the randomization code for the subject via the IWRS, by which system the unblinding will be captured. The unblinding and its cause will also be documented on the eCRF.

